6.3 Criteria for patient discontinuation

Patients may be discontinued from study treatment and assessments at any time. Specific reasons for discontinuing a patient for this study are:

- Voluntary discontinuation: participating patients are free to discontinue his/her participation in the study at any point in time, without prejudice to further treatment.
- Major protocol deviation
- Incorrect randomisation, i.e. the patient does not meet the required inclusion/exclusion criteria for the study
- Patient lost to follow-up
- Patient's non-compliance to study treatment and/or procedures

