CRP	C-reactive protein
DMC	Data monitoring committee
eGFR	Estimated glomerular filtration rate
GCP	Good clinical practice
ICH	International Conference on Harmonisation
IVUS	Intravascular ultrasound
LDL	Low density lipoprotein
NT-proBNP	N-terminal pro-B-type natriuretic peptide
PCSK9	Proprotein convertase subtilisin/kexin type 9
SAE	Serious adverse event
SUSAR	Suspected unexpected serious adverse reaction
TnT	Cardiac troponin T

Assessment	A procedure used to generate data required by the study
Control; control drug	A study drug used as a comparator to reduce assessment bias, preserve blinding of investigational drug, assess internal study validity, and/or evaluate comparative effects of the investigational drug
Enrolment	Point/time of patient entry into the study; the point at which informed consent must be obtained (i.e., prior to starting any of the procedures described in the protocol)
Investigational drug	The study drugs whose properties are being tested in the study; this definition is consistent with US CFR 21 Section 312.3 and is synonymous with "investigational new drug."
Randomisation number	A unique identifier on the label of each medication package in studies that dispense medication using an IVR system
Patient number	A unique identifier assigned to each patient who enrols in the study. In the EVOLVD study, the patient number equals the randomisation number
Phase	A major subdivision of the study timeline; begins and ends with major study milestones such as enrolment, randomisation, completion of treatment, etc.
Period	A minor subdivision of the study timeline; divides phases into smaller functional segments
Premature patient withdrawal	Point/time when the patient exits from the study prior to the planned completion of all study drug administration and assessments; at this time all study drug administration is discontinued and no further assessments are planned
Randomisation number	A unique identifier assigned to each randomised patient, corresponding to a specific treatment group assignment
Study drug	Any drug administered to the patient as part of the required study procedures; includes investigational drug and any control drugs
Study drug discontinuation	Point/time when patient permanently stops taking study drug for any reason; may or may not also be the point/time of premature patient withdrawal

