6.4 Procedures for discontinuation

6.4.1 Study drug discontinuation

The study participants may discontinue study drug treatment at any time according to their preferences. The investigator may also advise study drug discontinuation in case of side effects, if adverse effects of the treatment are suspected, or if contraindications to the continued use of evolocumab arise. Study drug discontinuation and the reason why must be documented in the eCRF as well as in the hospital record. Efforts should be made to make ensure that adherence to the study protocol is kept up even though the patient no longer takes the study drug. All available data will be used in the intention to treat analysis, unless the patient specifically disagrees to let the investigator use his or her data.

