10.3 Population for Analysis

The following populations will be considered for the analyses:

- Intention to treat (ITT) population: All randomised participants, regardless of protocol adherence.
- Safety population: All patients who have been enrolled in the trial, and who have received at least one dose of the investigational medicinal product (evolocumab or placebo).
- Per-protocol population (PP): Includes all subjects who have completed 12 months of treatment.

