10.5 Statistical analysis

All statistical tests will be performed using a two-sided 5 % level of significance. Continuous efficacy variables will be analysed using baseline-adjusted ANCOVA for comparisons between the treatment arms. If necessary, values will be log-transformed to meet the assumptions of the tests. All analyses will primarily be analysed according to the intention-to-treat principle. The number of major clinical events will be analysed using descriptive statistics. Between-group differences in ordinal categorical variables, such as NYHA class, will be analysed using ordinal logistic regression, whereas the count variables will be assessed by Poisson regression. Demographic, efficacy and safety data will be summarised by treatment group using means, minimums, medians, maximums, interquartile ranges and standard deviations for continuous variables and frequency counts and percentages for categorical variables. Per protocol analyses will be performed using the same methods as for the intention-to-treat analyses.

The primary endpoint, the between-group difference in the baseline-adjusted intima thickness at 12 months, will be calculated by baseline-adjusted ANCOVA according to the intention-to-treat principle, the statistical null-hypothesis being that the intima thickness does not differ between the two treatment arms. Secondary analyses will be made according to the per-protocol-principle as baseline-adjusted absolute values after end-of-treatment.

Key, secondary endpoints:

The secondary endpoints "Percent atheroma volume as measured by IVUS" and "Cardiac allograft vasculopathy" will be tested, at a two-sided alpha level of 0.05, in a hierarchical fashion. The baseline-adjusted between-group difference in the atheroma volume, eGFR, quality of life, and biomarkers reflecting cardiac function, blood lipids, and inflammation will be calculated by ANCOVA according to the intention to treat principle. The statistical null-hypotheses are that the changes in these characteristics do not differ between patients allocated to evolocumab and patients allocated to placebo.

Secondary per protocol analyses will be performed using the same methods as for the intentionto-treat analyses. Exploratory analyses will be made for efficacy variables stratified by centre.

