9.2 Populations for analysis

9.2.1 Full analysis set (modified intention-to-treat population)

The full analysis set (FAS) will include all patients who were randomised and who (irrespective of receipt of actual treatment) had intracoronary ultrasound adequate for the determination of coronary intima thickness at baseline and at the 12 months follow-up. The adequacy of the ultrasound examination must be determined before database lock and the randomisation code is opened. The primary analysis of the primary endpoint (and all secondary endpoints) will be carried out on the FAS.

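### Protocol 6.3 lets sites end outcome assessment for non-compliance, protocol deviation or ineligibility, which can select the primary analysis on adherence after randomisation

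*Protocol*

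**What the plan says.** **Rules on leaving the study**

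- Protocol 6.3 opens: "Patients may be discontinued from study treatment and assessments at any time". Its specific reasons include "Major protocol deviation", randomisation of a patient who did not meet the eligibility criteria, and "Patient's non-compliance to study treatment and/or procedures". Voluntary discontinuation and loss to follow-up are listed alongside them.
- The protocol glossary says of premature patient withdrawal: "at this time all study drug administration is discontinued and no further assessments are planned". A separate entry defines study drug discontinuation and notes that it need not coincide with withdrawal.
- Protocol 6.4.1, on stopping study drug, asks for efforts so that "adherence to the study protocol is kept up even though the patient no longer takes the study drug".
- Protocol 6.4.2 asks for a final assessment of withdrawn patients where possible and says that they will be counted in the intention-to-treat analysis.
- Protocol 7.1.1 allows an early second IVUS in patients who cannot finish 12 months, but only after at least 6 months of study drug.

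**Rules on the analysis**

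- Protocol 10.3 defines the intention-to-treat population as "All randomised participants, regardless of protocol adherence". Under 10.5 the primary endpoint "will be calculated by baseline-adjusted ANCOVA according to the intention-to-treat principle", with missing data omitted.
- SAP 9.2.1 makes the full analysis set the primary set. It takes randomised patients whether or not they received treatment, provided they "had intracoronary ultrasound adequate for the determination of coronary intima thickness at baseline and at the 12 months follow-up". SAP 9.4 rules out imputation in the primary analysis. SAP 11.4 adds three imputation scenarios as sensitivity analyses.

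**The concern.** Non-compliance, a protocol deviation and late-discovered ineligibility are reasons why a patient may no longer follow the treatment plan. They do not in themselves mean that the patient refuses, or cannot have, an outcome measurement. Section 6.3 nevertheless treats them as grounds for ending assessments too.

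The analysis rules turn that choice into an exclusion. Without a 12-month scan the patient is not in the full analysis set, and nothing in the primary analysis restores them. Whether a randomised patient counts can then depend on behaviour after randomisation, which is what an intention-to-treat analysis is meant to avoid. The full analysis set would move towards the per-protocol set, which SAP 9.2.2 already provides separately. A scan not taken cannot be recovered at the analysis stage.

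**Working it through.** **1. Does a patient closed out under 6.3 leave the primary analysis?** Take a patient removed from assessments for non-compliance before the second IVUS.

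- Protocol 6.4.1 asks for continued follow-up, but it is written for stopping study drug. Nothing says whether 6.3 or 6.4.1 governs a patient who fits both.
- Protocol 6.4.2 asks for a final assessment only where possible. Its promise to include withdrawn patients cannot be met in a set that requires a follow-up scan they do not have.
- Protocol 7.1.1 offers an early scan only after 6 months of drug, so a patient removed at month 4 is not covered.
- SAP 9.2.1 and 9.4 then exclude the patient, without imputation.

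So the patient is excluded if the site uses the permission. The permission is worded as optional.

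**2. The plan's own figure.** Inputs from Protocol 10.1: difference 0.05 mm, SD 0.09 mm, two-sided 5%, power 80%.

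n per arm = 2 × (1.96 + 0.8416)² × 0.09² / 0.05² = 50.9, so 51. The stated 51 per arm is reproduced and is not in question.

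**3. Size of the possible shift.** Protocol 10.1 takes progression of 0.08 mm and 0.03 mm in the two arms of an earlier everolimus trial as the basis for its 0.05 mm difference. Assume that:

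- a share f of each arm is removed before the 12-month IVUS;
- removed evolocumab patients progress like placebo patients (0.08 mm);
- removed placebo patients progress like other placebo patients.

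Effect in all randomised patients = 0.08 − [(1 − f) × 0.03 + f × 0.08] = 0.05 × (1 − f). The full analysis set still shows 0.050 mm.

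| f (assumed) | All randomised, mm | Full analysis set, mm | Ratio | Difference, mm |
|---|---|---|---|---|
| 2% | 0.049 | 0.050 | 1.02 | 0.001 |
| 5% | 0.0475 | 0.050 | 1.05 | 0.0025 |
| 10% | 0.045 | 0.050 | 1.11 | 0.005 |

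**4. Against the precision of the trial.** With 60 completers per arm, SE = 0.09 × √(2/60) = 0.0164 mm. The shift is 0.0025/0.0164 = 0.15 SE at 5% and 0.005/0.0164 = 0.30 SE at 10%.

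**5. Against the dropout allowance.** The plan allows 130 − 120 = 10 losses (7.7%). Removing 5% per arm is 0.05 × 130 = 6.5 patients. Removing 10% is 13, more than the whole allowance before any death or withdrawal of consent. The 10% row is therefore an upper end.

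**The case against.** The case against is substantial, and most of it limits the size of the point.

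- **The wording is permissive.** A reader might infer that the rules contradict each other and cannot all be followed. The documents do not support this: a site that stops drug and continues visits satisfies 6.3, 6.4.1 and 10.3 together. The fault is an unresolved ambiguity.
- **The plan expects non-adherent patients to stay.** Someone who merely stops injecting falls under 6.4.1. The glossary separates stopping drug from withdrawal, SAP 9.2.1 keeps patients regardless of treatment received, and SAP 10.4 reports compliers and non-compliers by arm. A reader might infer that the primary analysis will be enriched for compliers. The documents support only that it can be.
- **No removal rate is given.** Zero drug effect in partly treated patients is an extreme assumption. A reader might also infer a raised false-positive rate, but with equal removal of comparable patients there is no bias when the drug has no effect. Unequal removal has no source in the documents: the trial is double-blind, lipid results are withheld, and SAP 11.4 does not expect treatment to affect dropout.
- **The scan is not routine care.** Angiography at one year is routine (Protocol 6.2.4), but IVUS is added for the study (Protocol 1.4). Patients who decline procedures may give no scan whatever 6.3 says.
- **Removals would be visible.** SAP 9.4 and 10.1 report dropout by arm, reasons, and baseline data for patients with and without endpoint data. SAP 11.4 stress-tests the result.

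What remains is that none of this withdraws the permission in 6.3 or returns a removed patient to the primary analysis. The tabulations and scenarios show the gap and put assumed values in it. They cannot supply a scan that could have been taken.

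**Conclusion.** The point holds as a permission that can do harm. Section 6.3 lets sites end assessments for reasons tied to adherence or eligibility, and the full analysis set then drops those patients, contrary to the protocol's own definition of intention to treat and to the aim of 6.4.1.

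The likely size is modest: an effect about 5% to 11% too large, or 0.15 to 0.30 of a standard error. That range rests on three assumptions that the documents do not supply: removal of 5% to 10% per arm, removed evolocumab patients progressing like placebo patients, and an effect of 0.05 mm in those who remain. If sites never use the permission, the effect is nil. The sample size is unaffected. The reason to act is that the loss is avoidable and cannot be repaired after the fact.

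**What to change.** - **Protocol 6.3:** separate stopping study drug from ending assessments. State that major protocol deviation, incorrect randomisation and non-compliance do not by themselves end follow-up.
- **Who stays:** such patients keep scheduled visits, event collection and the 12-month IVUS unless they withdraw consent, die or are lost to follow-up.
- **Exception:** where angiography with IVUS is contraindicated, the scan is omitted and the other assessments continue. This is needed because incorrect randomisation includes failing the criterion in Protocol 4.3 on contraindications to that procedure.
- **Alignment:** bring the glossary entry on premature withdrawal and Protocol 6.4.2 into line with the new 6.3. The rules on stopping study drug stay as they are.

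The cost is a wording change and a letter to sites, some follow-up effort, and a study-specific IVUS in a few non-adherent patients. The effect estimate may be slightly smaller, because it would then describe more of those randomised.

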6.4 Procedures for discontinuation

6.4.1 Study drug discontinuation

The study participants may discontinue study drug treatment at any time according to their preferences. The investigator may also advise study drug discontinuation in case of side effects, if adverse effects of the treatment are suspected, or if contraindications to the continued use of evolocumab arise. Study drug discontinuation and the reason why must be documented in the eCRF as well as in the hospital record. Efforts should be made to make ensure that adherence to the study protocol is kept up even though the patient no longer takes the study drug. All available data will be used in the intention to treat analysis, unless the patient specifically disagrees to let the investigator use his or her data.

6.4.2 Patient discontinuation

Patient withdrawal must be documented in the CRF as well as in hospital records. If possible, a final assessment should be obtained (end of study visit). The reason for discontinuation is recorded. The investigator is obliged to follow up any significant adverse events until the outcome either is recovered or resolved, recovering/resolving, not recovered/not resolved, recovered/resolved with sequelae, fatal or unknown. Patients who withdraw will be included in the intention-to treat analysis.

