Safety analyses will include tabulation of type and frequency of all adverse events. Any serious adverse events will be reported with comprehensive narratives. Any value of safety laboratory parameters outside normal ranges will be identified.

Missing data will be omitted from analyses, i.e. there will be no imputation or estimation of missing values. However, a comparison of the baseline characteristics of those with an intima thickness measurement at 12 months and the baseline characteristics of those without a value will be performed to assess any bias introduced due to missing data. Statistical analyses will be performed in IBM SPSS Statistics version 21 or later.

11 Study management

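### The protocol promises an all-randomised ITT primary analysis that includes withdrawn patients, but the planned analysis keeps only patients with usable scans at baseline and 12 months

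*Protocol*

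**What the plan says.** The protocol describes an all-randomised analysis:

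- Protocol 6.4.2, on withdrawal: "Patients who withdraw will be included in the intention-to treat analysis". A final assessment is sought only where possible.
- Protocol 10.3, ITT population: "All randomised participants, regardless of protocol adherence".
- Protocol 10.5: the between-group difference in the primary endpoint "will be calculated by baseline-adjusted ANCOVA according to the intention-to-treat principle".
- Protocol 6.4.1: for patients who stop study drug, whatever data exist go into the ITT analysis unless the patient objects.

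The rules that decide who is actually analysed are narrower:

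- Protocol 10.5: "Missing data will be omitted from analyses, i.e. there will be no imputation or estimation of missing values".
- SAP 9.2.1 labels its full analysis set (FAS) as modified intention-to-treat. It admits randomised patients who "had intracoronary ultrasound adequate for the determination of coronary intima thickness at baseline and at the 12 months follow-up". It then says: "The primary analysis of the primary endpoint (and all secondary endpoints) will be carried out on the FAS".
- SAP 9.4 repeats that the primary analyses use no imputation.
- SAP 9.2 defines a FAS, a per-protocol set and a safety set. There is no all-randomised efficacy set.

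Three provisions soften this. Protocol 7.1.1 allows the second scan at discontinuation after at least 6 months of study drug. SAP 9.4 compares baseline data of patients with and without endpoint data and describes dropout by arm. SAP 11.4 adds three imputation scenarios for the primary endpoint.

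**The concern.** The two governing documents name different primary populations, and the property that the protocol states for the primary test is not delivered. ITT keeps patients in the comparison whatever happens after randomisation. Here, entry to the primary analysis depends on a post-randomisation event, a readable 12-month scan. Protocol 6.3 lists several post-randomisation routes out of treatment and assessments, such as non-compliance, protocol deviation and loss to follow-up. The protocol's glossary defines premature withdrawal as the point after which no assessments are planned. A withdrawn patient without a second scan is thus an ordinary case.

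The same filter reaches the repeated measures. SAP 11.3 fits mixed models to LDL, NT-proBNP and TnT, and the table in SAP 6.2 assigns eGFR to the same method. These models can use partial follow-up. Because SAP 9.2.1 applies the FAS to all secondary endpoints, a patient with several LDL values but no 12-month scan is dropped anyway, which does not sit with Protocol 6.4.1.

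**Working it through.** **1. The plan's own figure.** Inputs (Protocol 10.1, SAP 8): difference 0.05 mm, SD 0.09 mm, two-sided 5%, 80% power.
n per arm = 2 × (1.960 + 0.842)² × 0.09² / 0.05² = 50.9, so 51. The stated 51 is reproduced. At 60 per arm (120 completers) power is 86%. The sample size is not at fault.

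**2. Who is left out.** Take a withdrawn patient with no usable second scan:

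| Analysis | Is this patient in it? |
|---|---|
| ITT as described in Protocol 6.4.2, 10.3 | Yes |
| Primary ANCOVA under the omission rule in Protocol 10.5 | No |
| Primary ANCOVA on the FAS (SAP 9.2.1, 11.2) | No |
| SAP-listed secondary endpoints, including mixed models | No |
| Per-protocol set (SAP 9.2.2) | No |
| SAP 11.4 scenarios, primary endpoint | Yes, as a sensitivity analysis (scenarios 1 and 2 need a baseline scan) |
| Safety set (SAP 9.2.3) | Yes, if treated |

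**3. How many.** 130 randomised, 5-10% dropout (Protocol 10.1): 130 × 0.05 = 6.5 and 130 × 0.10 = 13. The planned step from 130 to 120 is 10 patients, 7.7%. These are maxima for dropouts, since some may have a usable second scan. Unreadable scans in patients who stay would add to the exclusions, but the documents give no rate.

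**4. Effect on the estimate.** Let d be the fraction missing in an arm and e the amount by which the missing patients' mean change exceeds that of the observed patients. The arm's all-randomised mean is then the observed mean plus d × e, so
all-randomised difference − complete-case difference = d_E × e_E − d_P × e_P
(E evolocumab, P placebo).

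*Assumption:* equal dropout in both arms, e_P = 0, and e_E = 0.09 mm in either direction. One SD is the size of shift used in SAP 11.4.

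| Dropout | Shift (mm) | Share of 0.05 mm | Rejection rate if there is no effect in all randomised | Power at 0.05 mm on those left, no shift |
|---|---|---|---|---|
| 5% | 0.05 × 0.09 = 0.0045 | 9% | 5.9% | 87% |
| 7.7% | 0.077 × 0.09 = 0.0069 | 14% | 7.1% | 86% |
| 10% | 0.10 × 0.09 = 0.0090 | 18% | 8.4% | 85% |

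The rejection rates use SE = 0.09 × √(2/n) with n = 65 × (1 − d). If e_E = e_P and d_E = d_P, the shift is zero.

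**5. What SAP 11.4 would show.** *Assumption:* observed mean changes of 0.03 mm (evolocumab) and 0.08 mm (placebo), overall mean 0.055 mm, SD 0.09 mm. At 10% missing:

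- Placebo, all scenarios: 0.9 × 0.08 + 0.1 × 0.055 = 0.0775.
- Best case: 0.9 × 0.03 + 0.1 × (0.055 − 0.09) = 0.0235; difference −0.054.
- Worst case: 0.9 × 0.03 + 0.1 × (0.055 + 0.09) = 0.0415; difference −0.036.
- Overall mean: 0.9 × 0.03 + 0.1 × 0.055 = 0.0325; difference −0.045.

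At 7.7% missing the three differences are −0.053, −0.039 and −0.046 mm.

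**The case against.** The strongest reply is that this is a labelling mismatch which the SAP has largely dealt with. Much of that reply stands.

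- A reader might infer that the trial is set to report an ITT result it does not have. The SAP does not support this: it calls the FAS modified intention-to-treat, and Protocol 10.4 lets the plan change until database lock, with deviations justified in the study report. The protocol's wording still differs.
- A reader might infer that withdrawn patients vanish altogether. They do not. Treated patients count in the safety set, where adverse events and rejections are reported, and SAP 11.4 brings missing patients back for the primary endpoint.
- A reader might infer a bias in favour of evolocumab. SAP 11.4 says the intervention is not expected to affect dropout, and neither document gives a direction. The calculated shift needs dropouts that differ in one arm only.
- The plan already tests a 1 SD worst case, and step 5 shows that it moves the estimate by more (from −0.050 to −0.036 mm at 10%) than the shift in step 4.
- A reader might assume that months 1-9 data are complete for withdrawn patients. By the glossary definition, data stop at withdrawal. Protocol 1.1 links cholesterol to allograft coronary disease, but the documents do not show that eGFR, NT-proBNP or TnT predicts 12-month thickness.

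Some of the concern survives. The SAP 11.4 scenarios impute fixed values and treat them as known, so their standard errors are too small. The scenario named for no change imputes the overall mean at each time point, which is not zero change. None is a missing-at-random analysis of all randomised patients. The early-scan route is partial, and SAP 9.2.1 does not say whether such a scan meets its 12-month condition.

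**Conclusion.** The inconsistency is in the text and needs no assumption: the protocol promises that withdrawn patients are in the primary analysis, and the operative rules exclude those without a usable second scan. The primary result is a complete-case, modified ITT result. SAP 11.4 itself accepts that dropout is unlikely to be completely at random and may bias the result.

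The size is modest. The 9-18% shift is an illustration that rests on no dropout having a usable second scan, equal dropout in both arms, and a 1 SD departure in the evolocumab arm alone. It could go either way and would be near zero if dropouts were alike in number and kind in the two arms. Power stays at about 85-87%, so the issue is possible bias and correct description, not sample size. The documents do not support reading it as proof of a biased trial or of a false claim. They do support correcting the wording and adding a better missing-data analysis before the code is opened.

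**What to change.** 1. **Reconcile the population.** Align Protocol 6.4.2, 10.3 and 10.5 with SAP 9.2.1, so that the primary result is called modified ITT (complete-case) in both documents and in reports. State that patients who withdraw without an adequate second scan are outside it. State whether an early second scan under Protocol 7.1.1 counts for the FAS. Confine the no-imputation rule in Protocol 10.5 to the primary analysis, since SAP 11.4 already imputes.
2. **Add one sensitivity analysis to SAP 11.4.** In all randomised patients, multiply impute 12-month thickness by arm from baseline thickness, centre and a small prespecified set of on-study values available before dropout (for example last LDL). Keep the set small, because each arm has only about 65 patients. Fit the same ANCOVA and combine by Rubin's rules. State how deaths and missing baseline scans are handled. Report it beside the FAS result and the existing scenarios.
3. **Widen the mixed models.** Fit the SAP 11.3 models for LDL, eGFR, NT-proBNP and TnT in all randomised patients with any measurement, not only those with a 12-month scan.

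Cost: a document update, which for the protocol goes through the amendment procedure in Protocol 11.3; one more analysis; and a headline result that cannot be called ITT. No new patients or data are needed.
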